## 1 PURPOSE/HYPOTHESES

### 1.1 Primary Hypothesis

The primary hypothesis is that Theracurmin treatment can decrease the rate of Revised ALS Functional Rating Scale (ALSFRS-R) progression by 50% relative to matched historical controls.

### 1.2 Secondary Hypotheses

Secondary hypotheses are as follows:

1. Theracurmin can increase the frequency of ALS reversals (defined by an improvement of 4 or more points in the ALSFRS-R over the course of 6 months) from 2-5% (observed spontaneously) to at least 10%.
2. Theracurmin can alter the fecal microbiome in patients with ALS.
3. The fecal microbiome of patients with ALS is significantly different from matched control subjects.
4. The fecal microbiome of patients with ALS is significantly different between subgroups with differing clinical features including sporadic vs. familial, anatomical location of symptom onset, and rate of progression as measured on the ASLFRS-R.
5. The novel features of this pilot trial will be associated with improved participant enrollment compared to prior more traditional ALS trials where enrollment is 2 participants per site per month.
6. The novel features of this pilot trial will be associated with improved participant retention compared to prior more traditional ALS trials where the dropout rate is 22% at 12 months.
7. The novel features of this pilot trial will be associated with improved participant compliance compared to prior more traditional ALS trials.

## 2 BACKGROUND

### 2.1 Amyotrophic Lateral Sclerosis (ALS) and Its Treatment

ALS is a devastating motor neuron disease that causes rapidly progressive muscle weakness, disability and premature death. In spite of a large number of attempted ALS trials, there are no significant disease-modifying therapies for this condition (1).

### 2.2 Failure of Previous Classically Designed ALS Trials

There are several reasons that previous ALS trials may have failed. First, the hypotheses could have been wrong. The hypotheses for many prior trials came from observations made in animal models of familial ALS (1). How well the animal models predict human ALS, the vast majority of which is not familial, has been called into question (2). Second, the dosing in previous ALS trials may not have been adequate. Indeed, most ALS trials have not even employed pharmacodynamic biomarkers to test their dosing regimen (3). In addition to these problems,

ALS trials are often challenged by slow enrollment (4) and poor retention (5). While some of the enrollment and retention issues may have to do with misconceptions on the part of enrolling clinicians and potential participants (4), patients with ALS do become more disabled over time, and study burdens, including trips to the study site, may eventually become impossible to bear.

### 2.3 Success of Previous Hybrid Virtual/Remote Trial

We previously conducted an open-label, single-center, hybrid-virtual 12-month trial of Lunasin for patients with ALS (6). This single-center trial featured broad inclusion criteria, historical controls, mostly virtual data collection, and real-time results. Participants measured their ALSFRS-R score, weight and perceived efficacy, and recorded these monthly on PatientsLikeMe (PLM; an online platform described section 2.7). ALSFRS-R decline was compared to historical controls. For each enrolled participant, PLM identified 3 historical controls matched according to pre-treatment ALSFRS-R progression, as in their previous Lithium study (7). We had 90% power to detect 50% slowing in decline of ALSFRS-R scores.

Although there were no significant differences in ALSFRS-R ( $p=0.99$ ) between study participants and historical controls, the study's outcomes suggested that there is utility and internal validity in a virtual trial model. Enrollment rate was 9.1 participants per site per month, which is the fastest rate of any ALS trial in history. As in most ALS trials, our 50 participants were primarily white (94%) males (58%), mean age of 60, limb onset disease (82%), taking riluzole (60%). However, our participants had longer disease duration than those in most trials, and several had non-invasive ventilation, PEG and/or tracheostomy, which are traditional exclusion criteria. This trial population was therefore more representative of the population seen in ALS clinics. In spite of enrolling patients with longer and more advanced disease, the survivor retention rate was 84%, while the survivor retention rate in traditional ALS trials is 78% (5).

We also looked at the accuracy of patient recorded ALSFRS-R and weight measurements. Lin's concordance (C) showed high agreement between coordinator and participant derived ALSFRS-R and weight respectively at month 1 ( $C=0.9939, 0.9947$ ) and month 12 visits ( $C=0.9428, 0.9905$ ). These results suggest that participant recorded ALSFRS-R scores and weight are sufficiently accurate to be used in a clinical trial.

Compliance with study protocol (assessed by the percentage of patients who logged onto PLM every month and entered at least 2 of the 3 key outcomes) was 88% or greater for each of the first 6 months, but then began to decline, eventually reaching only 55% at 12 months. This suggests that a 6 month virtual trial design may allow for high compliance throughout the entire study duration.

### 2.4 Curcumin

Curcumin is a chemical compound that is one of three curcuminoids found in the culinary spice turmeric. Curcumin has been studied in a wide variety of neurologic diseases and is purported to have many bioactive properties. It is widely available as a dietary supplement in multiple formulations from many commercial companies (8). The treatment Theracurmin utilized in this study is a formulation of curcumin (see section 3.2.1).

## 2.5 ALS Reversals on Curcumin

ALSUntangled is a consortium of ALS clinicians and researchers that review alternative and off-label treatments on behalf of patients with ALS (9). ALSUntangled recently reported on 3 patients with a validated diagnosis of ALS, whom experienced an ALS reversal while taking a supplement regimen containing curcumin (8). Several other patients with ALS have also reported improvements on a curcumin regimens, though records were not obtainable to validate these (8).

## 2.6 How Curcumin Could Influence ALS

We have published a review describing multiple biological mechanisms through which curcumin could influence ALS progression (8). In this study we are going to focus Theracurmin's potential effects on the fecal microbiome.

### 2.6.1 *Alterations of the Fecal Microbiome*

As in Parkinson's disease (10), there is increasing recent evidence that abnormalities in the gut microbiome may play a role in ALS pathophysiology. In a mouse model of ALS, for example, dysbiosis and impaired intestinal tight junctions and permeability occur before symptom onset (11). Altering the mouse microbiome via germ-free conditions, broad spectrum antibiotics or introduction of specific bacteria (*Ruminococcus torques* or *Purabacteroides distasonis*) exacerbate the ALS phenotype (12). On the other hand, feeding the mice butyrate (13), a natural product of a healthy microbiome, or introduction of other specific bacteria (*Akkermansia muciniphilia*) (12) improve the ALS phenotype. Alteration of the intestinal microbiome in a worm model of ALS can also improve motor function (14). Three studies suggest that people with ALS have altered intestinal microbiomes compared to healthy controls (12, 15, 16); a fourth small study did not find such a difference (17).

The curcumin formulation used in Theracurmin has been shown to have the capability of altering the fecal microbiome in mice (18). If curcumin can lead to a more favorable fecal microbiome profile in patients with ALS, it may help to slow or reverse ALS progression.

## 2.7 PatientsLikeMe

PatientsLikeMe® (PLM; [www.patientslikeme.com](http://www.patientslikeme.com)) is an online platform that has demonstrated an ability to engage patients in learning about their conditions and building a large quantitative and qualitative database about patients' experiences of their conditions. PLM is a patient network with over 300,000 members comprising over 2000 different conditions founded by a family affected by ALS, and to date has conducted over 30 published studies in ALS including studying patient use of off-label treatments. Members who join the site with ALS are asked to complete a number of data fields including demographics, disease condition history, treatments, symptoms, weight, treatment evaluations and lab measurements (e.g. weight, forced vital capacity). In addition, a unique feature of the site is the ability of patients to complete a widely used patient reported outcome, the ALS Functional Rating Scale, Revised (ALSFRS-R) which allows patients to see their disease progression in context in visual form. Data capture is facilitated by a team of PhD scientists, nurses, and pharmacists that incorporate information from various medical databases (e.g. RxNorm, ICD-10, MEDDRA). The site also provides means of social support through a message board forum, private messages, and profile commenting. Online methods of

data capture have the potential to dramatically accelerate trial recruitment, provide more convenient means of data capture for patients, and minimize trial complexity by using matched historical controls in lieu of a placebo control group. Our previous lunasin study (see section 2.3) was conducted on the PLM platform and we will continue to utilize the PLM platform for this study.

### **3 DESIGN & PROCEDURES:**

#### **3.1 Design Overview**

This will be a 6-month, widely inclusive, largely remote/virtual, single-center, open-label pilot trial utilizing a historical control group. Following informed consent and screening, participants will take the intervention (see section 3.2.1) for 6-months. Treatment with the intervention Theracurmin HP and all study outcome measures and labs are being performed exclusively for research purposes. Collected data includes ALSFRS-R, fecal sample microbiome sampling, adverse events, and concomitant medications. Participants will be asked to register for an account on PLM with the help of the study coordinator. User IDs associated with their PLM account will be recorded by the study coordinator and shared with study staff at PLM. When registering, participants will have the opportunity to review PLM's terms and conditions (Appendix A) as well as their privacy policy (Appendix B). After the baseline video/telephone visit, participants will be asked to enter the following data: weight and height, Theracurmin treatment evaluations (Appendix C), ALSFRS-R score (Appendix D) and Thrive Questionnaires (Appendix E). Participants will be given the following study documents and materials shipped to their home:

A PLM bag (Appendix F) including:

1. Welcome letter (Appendix G)
2. Study One-Sheet (Appendix H)
3. Study drug
4. Microbiome kits
5. PatientsLikeMe gifts

#### **3.2 Study Drug**

##### **3.2.1 *Theracurmin HP***

The intervention is based on the twice daily dosage of Theracurmin 90 mg capsules used in a trial of patients with mild cognitive impairment (19). This dosage is similar to that used in a trial of patients with ALS using similar bioavailable version of curcumin (20). Our 6-month intervention consists of Theracurmin HP capsules containing 90 mg curcumin each that will be taken as one capsule twice daily. Each capsule contains 300 mg Theracurmin enhanced bioavailable water-dispersible turmeric rhizome complex providing 30% curcumin (90 mg). The content of Theracurmin HP has been independently certified by NSF International under NSF/ANSI 173 (21).

### **3.2.2 *Theracurmin HP Supply***

The product Theracurmin HP (referred to as Theracurmin throughout) will be obtained from Integrative Therapeutic (22). Products will be stored in [name] locked office at Duke University. At enrollment into the study, participants will be sent a 2-month supply of product. After the Week 3 video/telephone visit, participants will be sent an additional 4-month supply. Once this study ends, participants may elect to continue the Theracurmin by purchasing from third-party distributors and select health care professionals.

### **3.2.3 *Dose Adjustments and Holidays***

The investigator may temporarily reduce or stop administering the Theracurmin for adverse events. If the adverse event is mild or moderate, the dose may be reduced to 90mg once a day until the event improves. The investigator may then choose to resume the dosage of 90mg twice a day or maintain the participant at reduced dose. If a related event is serious or life threatening, the Theracurmin should be stopped and will not be re-challenged. One drug holiday will be allowed; the holiday can last no more than 7 days. All dose reductions and suspensions must be documented.

### **3.2.4 *Compliance***

The method to check compliance for study medication will be to ask the participants to record the amount of product left over at all internet PLM visits occurring after the intervention begins. No further compliance checks will be conducted.

### **3.2.5 *Concomitant Medications***

Throughout the study, investigators may prescribe any other concomitant medications or treatments deemed necessary to provide adequate supportive care, provided that they are not part of an active research study.

### **3.2.6 *Use of Riluzole and Edaravone***

The use of riluzole will be permitted during the study. Patients taking riluzole must be on a stable dose for 30 days prior to screening. The use of edaravone will also be permitted. Patients currently receiving edaravone infusions must have completed at least 2 cycles of infusions before enrolling.

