### 3.5.1 Inclusion Criteria

Each primary participant must meet all of the following criteria at screening and baseline (unless otherwise specified) to participate in the study:

1. Male or female, aged at least 18 years.
2. Sporadic or familial ALS diagnosed as possible, laboratory-supported probable, probable, or definite as defined by revised El Escorial criteria.
3. Patient is able to understand and express informed consent (in the opinion of the site investigator).
4. Patient has access to the Internet on a desktop computer, laptop, or tablet and has a working email address.
5. Patient or caregiver is willing and able to use a computer and enter data on a secure website.
6. Patient is able to read and write English.
7. Patient is expected to survive for the duration of the trial.
8. Women must not be pregnant (will have evidence of a negative pregnancy test obtained by local physician within past 7 days or be post-menopausal)
9. Women must not be able to become pregnant (e.g., post-menopausal, surgically sterile, or using adequate birth control methods) for the duration of the study and three months after study completion. Adequate contraception includes: abstinence, hormonal contraception (oral

contraception, implanted contraception, injected contraception or other hormonal contraception, for example patch or contraceptive ring), intrauterine device (IUD) in place for  $\geq 3$  months, barrier method in conjunction with spermicide, or another adequate method.

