### **3.5.2     *Exclusion Criteria***

Primary Participants will be excluded for any of the following:

1. Patient is taking other experimental treatments for ALS (those that are part of an active research study).
2. Prior side effects from curcumin or turmeric containing products
3. Patient has a medical or psychiatric illness that could in the investigator's opinion interfere with the patient's ability to participate in this study.
4. Pregnant women or women currently breastfeeding.
5. Life expectancy shorter than the duration of the trial.
6. Taking an antiplatelet agent or anticoagulant (due to the theoretically increased risk of bleeding from curcumin products)

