## **4 DATA ANALYSIS & STATISTICAL CONSIDERATIONS**

### **4.1.1 *Historical Controls***

For each enrolled participant, three matched historical controls will be identified from the PatientsLikeMe database. Participants will be matched according to their ALSFRS-R progression rate before they start on the Theracurmin (estimated by assuming their score was normal at 48 on the date of symptom onset). Full details of the matching process are described in a previous paper (7).

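### Riluzole and edaravone use is not stated to enter control selection or the primary t-test, so a net difference in use could be read as a Theracurmin effect or hide one

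*Combined protocol and SAP*

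**What the plan says.** Section 3.2.6 covers the two drugs. On riluzole it says "The use of riluzole will be permitted during the study" and "Patients taking riluzole must be on a stable dose for 30 days prior to screening". It permits edaravone as well, on the condition that "Patients currently receiving edaravone infusions must have completed at least 2 cycles of infusions before enrolling". Both conditions look back from entry and apply only to patients already on the drug. The section does not say how a start, stop or dose change after entry is to be handled.

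Section 4.1.1 describes the historical controls: "Participants will be matched according to their ALSFRS-R progression rate before they start on the Theracurmin". The rate is estimated by assuming a score of 48 at symptom onset. For full details of the matching the section refers to a previous paper, which is not part of the documents.

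Section 4.1.2 compares the progression rate of participants with that of controls by a t-test. It names no covariate and no sensitivity analysis.

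Medication data are collected. Sections 3.1, 3.4 and 3.4.3 and Table 1 have participants record concomitant medications or changes in them on PatientsLikeMe (PLM), and section 2.7 says that members with ALS are asked for their treatments. Section 4 describes no use of these data in the primary comparison.

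**The concern.** This is a single-arm trial set against historical controls, so randomisation does not balance other ALS treatment between the groups. Balance has to come from control selection or from the analysis, and the only variable named for either is the progression rate before treatment.

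That variable does part of the work at most. It averages decline from symptom onset to baseline. It cannot reflect a drug started after baseline, and it reflects only weakly one started shortly before. For a long-established user it already carries some of any drug effect.

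Suppose participants and controls differ in how many use, or newly start, riluzole or edaravone, and suppose either drug changes the rate of decline. The t-test would then count the resulting difference as part of the Theracurmin contrast. More use among participants would favour Theracurmin; more use among controls would work against it. At stake is how the primary result is read: a small p-value may be partly due to other treatment, and a null result may be partly due to treatment of the controls.

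**Working it through.** **Inputs from the documents**
- Mean decline of 11 points in 12 months, so 11/12 = 0.917 points/month; SD 8 points at 12 months (4.1.2).
- Target: half the mean rate, so 0.917/2 = 0.458 points/month. One-sided test, alpha 5%, power 90% (4.1.2).
- 50 participants with 15% dropout: 50 x 0.85 = 42.5, taken as 42 completers.
- Controls: 50 (4.1.2) or three per participant, so 150 (4.1.1). The two sections differ, so both are shown.
- 60% took riluzole in the predecessor trial (2.3). If that repeats, 50 x 0.40 = 20 participants fall outside the 30-day riluzole condition.

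**The plan's own figure.** n per group = 2 x (8 x (1.645 + 1.282)/5.5)^2 = 36.2, rounded up to 37. With dropout, 37/0.85 = 43.5, so 44. The stated 50 is not reproduced; it is larger than its listed inputs require. Nothing below depends on this.

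**Assumptions, not in the documents**
- f: the net share of participants starting one of the drugs, over and above the share among controls.
- s: the proportion by which the drug slows decline, taken to act for the whole 6 months.
- The SD of the monthly rate is 8/12 = 0.667.

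**Formulas**
- Bias = f x s x 0.917 points/month.
- SE = 0.667 x sqrt(1/42 + 1/n2), which is 0.1395 for n2 = 50 and 0.1164 for n2 = 150.
- One-sided type I error = 1 - Phi(1.645 - bias/SE).

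| f | s | Bias (points/month) | Share of 0.458 target | Type I error, 50 controls | Type I error, 150 controls |
|---|---|---|---|---|---|
| 5% | 10% | 0.0046 | 1% | 5.3% | 5.4% |
| 10% | 20% | 0.0183 | 4% | 6.5% | 6.8% |
| 20% | 33% | 0.0605 | 13% | 11.3% | 13.0% |
| 40% | 33% | 0.1210 | 26% | 21.8% | 27.3% |

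Second row written out for 50 controls: 0.10 x 0.20 x 0.917 = 0.0183; 0.0183/0.1395 = 0.131; 1 - Phi(1.514) = 6.5%.

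**The opposite direction.** Suppose the net excess is among controls, at 20% and 33%, and Theracurmin truly halves the rate. The observable difference is then 0.458 - 0.0605 = 0.398. Power is Phi(0.398/SE - 1.645). With 50 controls it falls from 94.9% to 88.6%; with 150, from 98.9% to 96.2%.

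**Reading the table.** The last row needs a net 20 of 50 participants to start a drug, which equals all the expected riluzole non-users. It is a bound, not a forecast. A start part-way through follow-up gives a smaller bias. A 6-month slope with an SD above 0.667 gives less type I inflation for the same bias. The formula also covers a difference in background use, but as an overestimate for established users, because matching on prior rate removes part of that effect.

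**The case against.** The strongest reply is that much of this is already covered or cannot be judged from the documents. Several points stand.

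- A reader might infer that a patient who began riluzole last week is eligible, because neither condition is in 3.5.1 or 3.5.2. That does not follow. Section 3.2.6 uses mandatory wording and binds by itself, and 3.5.1 does not claim to be exhaustive. The omission is a matter of layout.
- A reader might infer that controls are not matched on drug use. The documents do not show that. Section 4.1.1 is silent and defers to a paper not available here. What can be said is that the protocol does not state it.
- A reader might infer that the conditions exist to keep recent treatment changes out of the efficacy comparison, and that later starts defeat this. Section 3.2.6 gives no purpose, and its edaravone condition is a minimum exposure, not a stability rule.
- Section 3.2.5 lets investigators give other treatment for supportive care. It does not clearly extend to these two drugs, which have their own section.
- Controls may start these drugs too. Only the net difference matters, and its sign is unknown.
- Section 2.1 holds that no existing therapy modifies the disease to a significant degree, which favours small values of s.
- Medication data are already recorded, so the gap is in the analysis plan and not in data capture.

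None of this supplies the missing statement. The protocol still does not say whether drug status affects control selection, and the t-test as written cannot separate a net difference in drug use from the study treatment.

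**Conclusion.** The point holds as a gap in the primary analysis. The comparison is non-randomised and unadjusted, one matching variable is named, and treatment data that are already collected are not used. A net difference in riluzole or edaravone use could bias the result in either direction.

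The likely size is modest. At 10% net starters and 20% slowing, the bias is about 0.018 points/month, 4% of the targeted difference, and the one-sided type I error is 6.5-6.8% instead of 5%. At 20% and 33% it is 11-13%. These figures rest on assumed uptake and drug effect, a drug acting throughout follow-up and a rate SD of 8/12. Section 2.1 points to the lower end.

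It would go too far to conclude that such drug use could by itself produce the targeted halving: even the most extreme row of the table reaches only 26% of the target. The documents also do not support a claim that the bias must favour Theracurmin.

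**What to change.** 1. In 4.1.1 and 4.1.2, either match controls on riluzole and edaravone status at the index date, or adjust the primary comparison for that status. Adjustment could be a linear regression of progression rate on group, riluzole status and edaravone status in place of the unadjusted t-test. Define the index date for controls and take status from the PLM treatment fields. If the cited matching method already uses treatment status, say so in 4.1.1.
2. Pre-specify one supportive analysis of starts and stops after baseline, with the same rule for participants and controls. If scores are cut off at the change, state the limits: with scores about every 30 days from week 4, an early change leaves few observations, and the cut-off may be informative if those who change treatment are declining faster.
3. As an editorial tidy-up, cross-reference 3.2.6 in 3.5.1.

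The cost is protocol and analysis wording, a treatment-status variable in the PLM extract and one additional analysis. Matching would leave fewer candidate controls for edaravone users; where they are too few, adjust instead. No change is proposed to patient care or to which drugs are permitted.
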